3.4 Withdrawal and discontinuation

Participants can withdraw from the investigation at any time and without giving reasons. Participants will be excluded from the examination if an imminent injury or illness contraindications exercise or cold application.

4 STATISTICS AND METHODOLOGY

4.1. Statistical analysis plan and sample size calculation

Sample calculation

Before any data collection is carried out, case number planning and sample size calculation is necessary in order to obtain valid results. In clinical trials and animal experiments, this is even mandatory and is carefully reviewed before approval is granted (MDR, Annex XV, Chapter 1, Section 2.1, DIN EN ISO 14155:2021-05). Postoperative cryotherapy utilizing ice packs, cooling, or continuous cryotherapy devices reduced pain scores on the visual analogue scale and analgesic consumption in about half of the research studies comparing these outcomes against their control (no cryotherapy). The average initial VAS score after pain induction varies depending on the study and is an approximation of a baseline value of 4.73 ± 2.39 . A reduction in the VAS score after cold application was assumed to be an average of 47%. After taking into account the dropout rate of 10% and splitting into 3 randomized groups, a patient count of 15 subjects per study arm is considered statistically appropriate. The results were determined using the PASS 2023 version 23.0.1 software.

Numerical Results for Multiarm Tests for the Difference Between Treatment and Control Agents Assuming Equal Variance

Solve for:	Number of cases
Group distribution:	equal to ($N_c = N_1 = N_2 = \dots$)
Test Type:	T-Test
Hypothesis:	$H_0: \delta = 0$ vs. $H_1: \delta \neq 0$
Number of groups:	3
Bonferroni Correction:	none (divisor = 1)

Comparison	Target Strength	Real	Number of cases	Mean μ_i	Difference δ_i	Standard deviation σ	Alpha
Control			13	4,72		2,1	
vs. A	0,8	0,832 33	13	2,21	-2,51	2,1	0,05
vs. B	0,8	0,912 87	13	1,87	-2,85	2,1	0,05
Total	n/a	n/a	39	n/a	n/a	n/a	n/a

Comparison	The group involved in the comparison between the treatment and control shown in this report row. The comparison is made on the basis of the difference.
Test Strength	The desired test strength. Test strength is the probability of rejecting a false null hypothesis for this comparison. This test strength refers only to the comparison shown in this line.
Really. TS	The test strength that is really achieved.
N_i	The number of elements in the i th group. The total sample size is displayed in the last row of the column.
μ_i	The mean value of the i th group at which the test strength is calculated. The first row contains μ_c , the mean value of the control group.
δ_i	The difference between the i th treatment agent and the control agent ($\mu_i - \mu_c$) for which the test strength is calculated.
σ	The standard deviation of the responses within each group.
Alpha	The probability of rejecting the null hypothesis that the control mean is equal to the treatment mean described in this row.

Summary statements

A parallel 3-group design (with a control group and 2 treatment groups) is used to test whether the mean for each treatment group is different from the mean of the control group ($H_0: \delta = 0$ versus $H_1: \delta \neq 0, \delta = \mu_i - \mu_c$). The hypotheses are evaluated using two two-sided, two-sample methods. Bonferroni-adjusted t-tests with the same variance and an overall (experimental) Type I error rate (α) of 0.05. The common standard deviation for all groups is assumed to be 2.1. The mean value of the control group is assumed to be 4.72. The treatment means 2.21 and 1.87 with at least 80% test strength to be detected in each case. For the test, the (same) group sample size needed for each of the three groups (control and treatments) is 13 (39 subjects in total). The group sample sizes were calculated using PASS 2023, version 23.0.1.

Sample size taking into account the dropout rate

Group	Dropouts Abandonment Rate	Number of cases/group	Number of cases with drop-out rate	Number of abandoned participants
1 - 3	10%	13	15	2
Total	n/a	39	45	6

Taking into account the drop-out rate

Taking into account a dropout rate of 10%, the group sizes in each study arm should be 15 subjects.

Statistical approach to examine the primary endpoints

The statistical analysis is performed using IBM SPSS Statistics (version 27, IBM Corp., Armonk, NY, USA) and the significance level is set to $p < 0.05$.

In order to be able to determine the differences between groups, a repeated ANOVA analysis is carried out with a factor of 1: time (baseline, 24 hours, 48 hours, 72 hours) and a factor of 2:

intervention (group A, group B, group C) for the recovery parameters (inflammation values, muscle swelling, muscle soreness data, maximum voluntary isometric muscle contraction).

The examination is discontinued if the participants are intolerant to the local cold application. Participants in the IC and DC groups are instructed to cancel a cooling session and contact their contact immediately if they experience symptoms such as severe pain/discomfort as a result of the cooling.

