Number of Participants with Rationale	The study is planned with 3 study arms. The average initial VAS score after pain induction varies depending on the examination and is an approximation of an initial value of 4.73 ± 2.39 . A reduction in the VAS score after cold application was assumed to be an average of 47%. After taking into account the dropout rate of 10% and splitting into 3 randomized groups, a patient count of 15 subjects per study arm is considered statistically appropriate. The results were determined using the PASS 2023 version 23.0.1 software.
Intervention	The product "Cold Hot Pearls Maxi Pack" of the company Axanova AG is used for testing. This product has a gel bead filling that can be used for cold and heat applications. According to the manufacturer, the cold compresses must be stored in a freezer for at least 1 hour before they can be used. The cold pack can then be placed on the affected area on the fleece side, but for a maximum of 20 minutes in the same place.

	
In our study, there are 2 cooling groups:
 
The first group starts cooling immediately after the muscle soreness protocol.
 
The second group starts cooling 24 hours after the muscle soreness protocol.

Control Intervention	
The control group will not receive an intervention according to the muscle soreness protocol.

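### The sample size is justified by a 47% fall in VAS soreness, but the calculation behind it uses falls of 53% and 60%

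*Combined protocol and SAP*

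**What the plan says.** The synopsis (Number of Participants with Rationale) says the VAS score after pain induction "is an approximation of an initial value of 4.73 ± 2.39". It assumes an average reduction of 47% after cold application and concludes that "a patient count of 15 subjects per study arm is considered statistically appropriate". Section 4.1 repeats this: the score "is an approximation of a baseline value of 4.73 ± 2.39", and "A reduction in the VAS score after cold application was assumed to be an average of 47" per cent. It then adds: "The results were determined using the PASS 2023 version 23.0.1 software".

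The PASS table and summary statement that follow in section 4.1 use other inputs:

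- control mean 4.72;
- treatment means 2.21 (A) and 1.87 (B), so differences of −2.51 and −2.85;
- common SD 2.1, with σ defined as "The standard deviation of the responses within each group";
- 13 per arm, with a target power of 80% and achieved powers of 0.83233 (A) and 0.91287 (B).

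A 10% dropout rate then takes 13 to 15 per arm, 45 in total.

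The same section disagrees with itself on alpha. The Bonferroni entry in the table begins "none (divisor = 1", while the summary statement describes "Bonferroni-adjusted t-tests with the same variance and an overall (experimental) Type I error rate" of 0.05.

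**The concern.** This is the only sample-size justification in the documents. The effect given in words, in the synopsis and again in section 4.1, is smaller than either effect entered in the calculation, and the text presents that calculation as its result. The SD differs too: ± 2.39 beside the initial score, 2.1 in the table. No sentence says how 47% became 2.21 and 1.87, or where 2.1 comes from.

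Someone who reads only the synopsis would take 15 per arm to be adequate for a 47% reduction. If 47% is the intended effect, the 80% target of section 4.1 is missed at the number of completers the plan expects. A null result would then be read as coming from a better-powered comparison than it was.

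**Working it through.** **Inputs.** From the text: 4.73, ± 2.39, 47%. From the PASS table and summary: 4.72, 2.21, 1.87, SD 2.1, two-sided equal-variance t-tests, alpha 0.05, 13 per arm, 10% dropout.

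**Method.** Power of the two-sided two-sample t-test from the noncentral t distribution, with df = 2n − 2 and noncentrality δ / (σ√(2/n)). At n = 13, df = 24, the two-sided 5% critical value is 2.064, and σ√(2/n) = 2.1 × 0.3922 = 0.8237.

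**1. The plan's own figures.**

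- A: 2.51 / 0.8237 = 3.047, power 0.8323.
- B: 2.85 / 0.8237 = 3.460, power 0.9129.

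Both match the printed values. With n = 12, arm A has 0.799, so 13 is the smallest n that reaches 80%. 13 / 0.9 = 14.4, rounded up to 15. The table is correct for its inputs, and it was run without a Bonferroni correction.

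**2. The reductions in the table.**

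- A: 2.51 / 4.72 = 53.2%.
- B: 2.85 / 4.72 = 60.4%.
- Average: 56.8%, so averaging the arms does not give 47% either.

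**3. Power for the effect in the text.** 0.47 × 4.73 = 2.223 (0.47 × 4.72 = 2.218). At n = 13 the noncentrality is 2.223 / 0.8237 = 2.699. The table below uses alpha 0.05.

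| Evaluable per arm | δ = 2.223, SD 2.1 | δ = 2.223, SD 2.39 (sensitivity only) |
|---|---|---|
| 13 | 73.6% | 62.4% |
| 14 | 76.9% | 65.9% |
| 15 | 79.9% | 69.1% |

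With δ = 2.218 and SD 2.1, power at 13 per arm is 73.4%. Dropout of 10% from 15 leaves 15 × 0.9 = 13.5, so 13 to 14 is the expected range. With SD 2.1, 80% power needs 16 evaluable per arm; 16 / 0.9 = 17.8, so 18 enrolled per arm, or 54 in total.

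**4. Difference detectable with 80% power at 13 per arm, alpha 0.05.** With SD 2.1 it is 2.41 (51% of 4.72); with SD 2.39 it is 2.74 (58%). Both exceed 2.22.

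**5. If alpha is 0.025 per comparison, as the summary statement implies.** At 13 per arm:

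- 47% reduction: 62% (SD 2.1) or 50% (SD 2.39).
- The table's own arms: 74% (A) and 85% (B).
- Detectable difference: 2.68 (57% of 4.72) with SD 2.1, or 3.05 (65%) with SD 2.39.

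**6. Could 47% mean a reduction to 47%?** 2.21 / 4.72 = 46.8%, and 0.53 × 4.73 = 2.51, so arm A fits. Arm B does not: 1.87 / 4.72 = 39.6%. The two arms' means average 43.2% of control, so an average of 47% is not recovered this way either.

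**The case against.** The strongest reply is that one sentence is badly worded beside a complete calculation. The summary statement gives every powered input, and the result reproduces. If 47% should read as a reduction to 47%, arm A's difference and its 83% stand at the table's alpha, and arm B, with a larger difference, needs no more participants. This is plausible, but the documents do not confirm it, and it leaves arm B's mean and the SD of 2.1 unexplained. Even then, the synopsis and section 4.1 state the wrong effect.

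Second, 74% mixes the text's percentage with the table's SD. It also treats a fall from the initial score as a difference from control, which requires the control mean to stay near 4.73. Both are assumptions. The second is the plan's own in effect, since the table's control mean of 4.72 is almost the initial value. On the first, ± 2.39 is attached to the initial score and is not labelled an SD, so 2.1 is the fairer choice for the main figure; using 2.39 would make the shortfall larger.

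Third, the synopsis gives no power target, so its reader is told only that 15 per arm is adequate. That stands: the 80% appears in section 4.1 alone.

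Fourth, the shortfall is modest. That also stands: about 6 points at 13 per arm, 3 at 14, and almost none at 15.

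**Conclusion.** The concern holds. The stated effect (47%) and the powered effects (53% and 60%) contradict each other, and nothing in the documents links them. That finding needs no assumption. The powers of 83% and 91% are right for the table's inputs and should not be read as support for a 47% reduction.

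The size of the consequence is conditional. If a 47% reduction against a control mean of about 4.73 is intended, with SD 2.1 and two-sided alpha 0.05, each comparison with control has about 74% power at 13 evaluable per arm and 79.9% if all 15 complete. If a reduction to 47% was meant, arm A's 83% stands and the fault is in the wording. The documents do not show which applies. All these figures are for the two-sample t-test used in the sample-size calculation, not for the repeated-measures ANOVA planned for the analysis.

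**What to change.** Trace the source of the 47% (by or to), of arm B's mean of 1.87 and of the SD of 2.1. Then use one set of effect inputs in the synopsis, the text of section 4.1 and the PASS table.

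- **If a 47% reduction stands**, replace the power statement with, for example: *With 13 evaluable participants per arm, a difference of 2.22 and an SD of 2.1, each two-sided t-test against control has about 74% power at alpha 0.05.* Alternatively, give the difference detectable with 80% power: about 2.41 with SD 2.1, or 2.74 if the SD is 2.39.
- **If the table stands**, replace 47% with 53% (A) and 60% (B), and give the source of the SD of 2.1.
- **In either case**, keep ± 2.39, but label it as descriptive of the initial score or explain how it relates to 2.1.
- **Name the alpha** beside every figure, because section 4.1 gives two. At 0.025 per comparison and 13 per arm, the figures become 62% for a 47% reduction with SD 2.1 (detectable difference 2.68), or 74% (A) and 85% (B) for the table's means.
- **State the test**: these powers apply to the two-sample t-test, not to the repeated-measures ANOVA.

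Keep n=45. The cost is wording in the synopsis and section 4.1 and possibly a less favourable stated power. No participants are added, and endpoints and conduct do not change.

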2 INVESTIGATION OBJECTIVES AND DESIGN

2.1 Hypothesis and primary objective

The aim of this study is to investigate whether repeated, local cold applications have a positive impact on recovery compared to no intervention. Furthermore, it will be investigated whether cooling, which has been carried out immediately after the exertion, has a more positive influence on the recovery compared to refrigeration that has started 24 hours after the exertion. The ability to recover is determined on the basis of the following parameters: muscle soreness, inflammation levels, muscle swelling and maximum voluntary isometric contraction of the thigh muscles.

- H0A: There is no significant difference between repeated cold applications and the control intervention in terms of recovery capacity.
- H1A: There is a significant difference between repeated cold applications and the control intervention in terms of recovery capacity.

- H0A: There is no significant difference between immediate cold applications and delayed cold applications in terms of recovery.

H1A: There is a significant difference between immediate cold applications and delayed cold applications in terms of recovery.

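### The overall 5% error claim in section 4.1 covers only the two comparisons with control; immediate versus delayed cooling, listed under the primary objective, has no test, alpha or gate

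*Combined protocol and SAP*

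**What the plan says.** Section 2.1 (Hypothesis and primary objective) lists two pairs of hypotheses. One compares repeated cooling with control and does not separate the two cooling arms. The other compares immediate with delayed cooling; its alternative reads "There is a significant difference between immediate cold applications and delayed cold applications in terms of recovery". Neither pair is ranked as secondary or exploratory.

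Section 4.1, in the sample-size summary, describes a three-group design that "is used to test whether the mean for each treatment group is different from the mean of the control group". It continues: "The hypotheses are evaluated using two two-sided, two-sample methods", and calls these "Bonferroni-adjusted t-tests with the same variance and an overall (experimental) Type I error rate (α) of 0.05". The PASS table above that summary gives the Bonferroni setting as "none (divisor = 1" and shows alpha 0.05 on each row. The legend defines that alpha per comparison: "The probability of rejecting the null hypothesis that the control mean is equal to the treatment mean described in this row".

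The analysis paragraph of 4.1 says of the SPSS analysis "and the significance level is set to" p < 0.05. It then specifies a repeated-measures ANOVA with time (four levels) and intervention (three groups). It names no pairwise tests to follow the ANOVA and no adjustment for them.

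**The concern.** Three groups give three pairwise contrasts: A-C, B-C and A-B (C = control). The experiment-wise 5% is attached to the first two only. A-B answers the question of timing in the trial's title, yet no rule says at what level, or after what gate, it may be claimed.

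The practical consequence is an undefined result. An A-B p-value of 0.03 would count as confirmed at 0.05, would fail if 5% were split over three contrasts (0.05/3 = 0.0167), and would depend on another test if a gate applied. Unless the rule is written down beforehand, the choice could be made after the data are seen. The choice also affects power: some repairs leave 13 per arm adequate for A vs control and others do not.

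**Working it through.** **Inputs (section 4.1).** Control mean 4.72; treatment means 2.21 (A) and 1.87 (B); common SD 2.1; 13 per arm; two-sided tests; 80% target power; 10% dropout. The implied A-B difference is 2.21 − 1.87 = 0.34.

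**Step 1: reproduce the plan's power.** For a two-sample t-test with 24 degrees of freedom, the standard error of a difference is 2.1 × √(2/13) = 0.824. The noncentrality is 2.51/0.824 = 3.05 for A-C and 2.85/0.824 = 3.46 for B-C. Noncentral-t power:

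| Alpha per test | A-C | B-C |
|---|---|---|
| 0.05 | 0.83233 | 0.91287 |
| 0.025 (Bonferroni over two) | 0.740 | 0.850 |
| 0.0167 (Bonferroni over three) | 0.681 | 0.804 |

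The first row matches the PASS table exactly. The stated powers therefore used no Bonferroni correction, contrary to the summary sentence.

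**Step 2: false-claim rate over the contrasts.** Three normal groups of 13 were simulated with equal SD and no true differences, for one endpoint at one time (1,000,000 runs). Simulation keeps the correlation between contrasts that share an arm.

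| Reading | At least one false claim |
|---|---|
| Two control tests at 0.025, A-B not tested | 4.7% |
| Control tests at 0.025, A-B at 0.05 | 8.5% |
| Two control tests at 0.05, A-B not tested | 9.1% |
| All three at 0.05 | 12.2% |
| All three at 0.0167 | 4.4% |
| All three at 0.05, only after a significant three-group F test at 0.05 | 5.0% |

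As a check on the second row, the levels sum to 0.025 + 0.025 + 0.05 = 0.10 (upper bound), and independence would give 1 − 0.975² × 0.95 = 9.7%. With 15 per arm the results are practically the same.

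**Step 3: does the F gate protect each contrast?** With exactly three groups, either all means are equal, and the F test itself limits error to 5%, or at most one pair is equal, and only that one true null can be falsely rejected, at 0.05. Simulation with SD 2.1 throughout (400,000 runs) agrees: false A-B claims 5.0% when A = B and C differs; false A-C claims 5.0% when A = C and B differs.

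The error term matters if SDs differ. As an illustrative assumption, take SDs of 2.1, 2.1 and 1.2 for A, B and C, with A = B and C different. False A-B claims are then about 8.4% with the pooled ANOVA error but 5.0% with ordinary two-sample t-tests.

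**Step 4: power under the gate, on the plan's means, 13 per arm.** With two-sample t-tests: A-C 81.4%, B-C 88.1%, A-B 6.8%. With pooled error: A-C 82.3%, B-C 88.6%, A-B 6.9%. The F test itself is significant in 91% of trials. A-B power is low because its noncentrality is only 0.34/0.824 = 0.41; even an ungated test at 0.05 would need 600 per arm for 80% power.

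**The case against.** A reader might infer that A vs B is tested at the full 0.05, so that the plan's overall error is 8.5% as written. The documents do not support that. No section names an A vs B test or its level. The p < 0.05 introduces a three-group repeated-measures ANOVA, and if pairwise tests followed only a significant group test the rate would be about 5%. The 8.5% also needs the control tests to run at 0.025, whereas the table and the reproduced powers say 0.05, which leads to about 12%. So 8.5% is one conditional value within a range.

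The Bonferroni sentence sits in the sample-size summary and speaks only of comparisons with control. Read narrowly, it claims nothing about A-B. That is fair, but no other error statement covers A-B, and section 2.1 gives it primary standing. Section 2.1 introduces the timing question as an addition, which might hint at lower rank; its heading and the formal hypothesis pair point the other way.

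The cooling-versus-control hypothesis may mean both cooling arms pooled. The family would then be pooled cooling vs C plus A vs B, with a rate of about 9.6% at 0.05 each. That reading conflicts with 4.1, which tests each arm separately, and A-B still lies outside the 4.1 family.

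Finally, the F gate is not the only valid procedure, and it needs a single named endpoint value, which the plan does not currently choose. Both points stand.

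**Conclusion.** The concern holds as a gap in specification: the overall 5% in 4.1 does not extend to A vs B, and no rule elsewhere covers that contrast. Depending on the reading, the false-claim rate over the three contrasts is about 5%, 8.5% or 12%. These figures assume normal data, equal SDs, 13 per arm, no true differences, and one endpoint at one time. The several primary endpoints and the repeated time points add multiplicity that is separate and not counted here.

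The point should be settled before analysis. Sample size need not change if the gated procedure is used. Whatever procedure is chosen, the trial has almost no chance of showing a timing difference as small as its own planning means imply.

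**What to change.** In section 4.1:

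1. Name one endpoint and one time (or summary) value to which the error claim applies.
2. On that value, test the three-group difference with the F test at 0.05. Only if it is significant, test A-C, B-C and A-B each at 0.05 with two-sample t-tests. Use the pooled ANOVA error only if equal variances are reasonable.
3. Replace the Bonferroni sentence, or otherwise reconcile it with the divisor of 1 in the table.
4. State whether the cooling-versus-control hypothesis in 2.1 means each cooling arm or both arms pooled.
5. Restate power for this single-value comparison at 13 per arm: about 81-82% (A-C), 88-89% (B-C) and 7% (A-B at a difference of 0.34).

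Alternatively, keep Bonferroni over the two control comparisons and label A vs B exploratory, outside the 5% claim. Power is then 74% and 85%, so A-C misses the 80% target at 13 per arm. Meeting it needs 15 completers, or 15/0.9 = 16.7, rounded up to 17 enrolled per arm (51 in total).

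The gated version costs no extra participants or measurements: it needs a choice of endpoint value, new wording and one additional F test. Its downsides are that no pairwise claim is possible if the F test fails, and that stated power falls slightly, from 83% to 81-82% for A-C and from 91% to 88-89% for B-C.

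### The sample size summary claims Bonferroni-adjusted tests at an overall alpha of 0.05, but the calculation used no correction: either power for group A is 74%, or the familywise error is about 9%

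*Combined protocol and SAP*

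**What the plan says.** All of the relevant text is in section 4.1.

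- **Software output.** The Bonferroni row reads "none (divisor = 1"). Alpha is 0.05 for A versus control and again for B versus control. The achieved powers are 0.83233 and 0.91287 with 13 per group.
- **Glossary under the table.** Alpha is defined row by row: "The probability of rejecting the null hypothesis that the control mean is equal to the treatment mean described in this row". It is therefore a per-comparison level.
- **Summary statements, describing the same run.** "The hypotheses are evaluated using two two-sided, two-sample methods", and these are called "Bonferroni-adjusted t-tests with the same variance and an overall (experimental) Type I error rate (α) of 0.05". On power: "The treatment means 2.21 and 1.87 with at least 80% test strength to be detected in each case". On size: "group sample size needed for each of the three groups (control and treatments) is 13 (39 subjects in total").
- **Dropout table.** 13 per group is raised to 15 per group (45 in total) for 10% dropout. Section 4.2 says that drop-outs are not replaced.
- **Analysis paragraph.** The significance level is p < 0.05 for a repeated-measures ANOVA. No multiplicity adjustment is mentioned.

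**The concern.** With two comparisons, a Bonferroni adjustment to an overall 0.05 means a divisor of 2 and 0.025 per test. A divisor of 1 with 0.05 in each row is no adjustment. The summary and the table describe one calculation, so they cannot both be right.

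At stake is the only justification given for 45 subjects, and the threshold for the two comparisons with control. A contrast with p between 0.025 and 0.05 is positive under the table and negative under the summary. Because the analysis paragraph does not choose, the choice could be made after the results are seen.

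**Working it through.** **Inputs (section 4.1).** Control mean 4.72; treatment means 2.21 (A) and 1.87 (B), so the differences are 2.51 and 2.85; common SD 2.1; n = 13 per group; two-sided two-sample t-tests with equal variance, df = 2 × 13 − 2 = 24.

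**Formula.** The noncentrality is λ = δ / (SD × √(2/n)). Power is P(|T| > t_crit), where T is noncentral t with 24 df and noncentrality λ.

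- A: λ = 2.51 / (2.1 × √(2/13)) = 3.047
- B: λ = 2.85 / (2.1 × √(2/13)) = 3.460

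**Step 1: reproduce the plan's figures, then apply the claimed adjustment.**

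| Alpha per test | t_crit (24 df) | Power A | Power B |
|---|---|---|---|
| 0.05 (table) | 2.064 | 0.83233 | 0.91287 |
| 0.025 (Bonferroni, two tests) | 2.391 | 0.740 | 0.850 |

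The first row matches the printed powers to five decimals, so the calculation was run without adjustment. The second row is what the summary's wording implies.

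**Step 2: sample size if the adjustment is kept.** Power for A at 0.025 is 74.0% with 13 per group, 77.8% with 14 and 81.1% with 15. Reaching 80% takes 15 evaluable per arm. With 10% dropout, 15 / 0.9 = 16.7, so 17 enrolled per arm and 51 in total against 45 planned. The plan's own step, 13 / 0.9 = 14.4 rounded up to 15, is correct.

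**Step 3: familywise error if the adjustment is dropped.** Two independent tests at 0.05 would give 1 − 0.95² = 9.75%. The two tests share the control arm, which lowers this a little. Simulating both t-tests under no effect with 13 per group (1,000,000 replicates) gives about 9.1%. With Bonferroni at 0.025 the simulated value is 4.7%.

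**Step 4: an alternative that uses the shared control.** Dunnett's test of A and B against control, with variance pooled over the three arms (df = 39 − 3 = 36) and overall alpha 0.05, has a critical value of 2.30. Power with 13 per arm is 77.0% for A and 87.2% for B.

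**Side calculation.** The narrative in the same section gives different inputs: a 47% reduction from 4.73 with SD 2.39, so a difference of 0.47 × 4.73 = 2.22. With 13 per arm, power is 62% at 0.05 and 50% at 0.025. Most of the shortfall from 80% (about 18 of 30 points) comes from the mismatch in inputs and about 12 points from the adjustment. The present point does not rest on this.

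**The case against.** The strongest reply is that 74% and 9% describe two stand-alone t-tests in a sample size section, while the planned analysis is a repeated-measures ANOVA. One omnibus test per outcome at 0.05 does not carry a 9% error. That limit on scope is fair: the figures are not the ANOVA's operating characteristics. It does not remove the contradiction, because the summary itself says the hypotheses are evaluated with these t-tests, and the ANOVA paragraph does not say how A and B are to be compared with control or at what level.

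Second, the 74% assumes two losses in every arm. If all 15 enrolled per arm were evaluable, Bonferroni power would be 81.1% for A and 90.4% for B. This is correct, but 13 evaluable is the plan's own basis and drop-outs are not replaced. Only A falls short; B stays at 85%.

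Third, the simplest cure may be to delete the Bonferroni wording and call alpha per-comparison, as the glossary does. That would be consistent, but it gives up the overall 0.05 that the protocol now claims, and the protocol would have to say so.

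Finally, the table's own arithmetic is right. The fault lies between the table and the text that describes it.

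**Conclusion.** The concern holds: section 4.1 is wrong as written. With its own inputs (SD 2.1, differences 2.51 and 2.85, 13 evaluable per arm), the plan cannot have both 80% power for A and a Bonferroni-controlled overall error of 5%. If the summary governs, power for A is 74.0%, six points under the target, and B has 85.0%. If the table governs, the familywise error is about 9% against a stated 5%.

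The 9% covers only the two comparisons with control on a single outcome. The A-versus-B hypothesis in section 2.1 and the several primary endpoints in section 2.2 lie outside it. This must be corrected, because it affects the basis for the sample size and leaves the significance threshold open.

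**What to change.** 1. Keep the overall alpha of 0.05 for A versus C and B versus C, and set the Bonferroni divisor in the output to 2.
2. Restate power for 13 evaluable per arm as 74% (A) and 85% (B), and withdraw the claim of at least 80% in each case. Alternatively, specify Dunnett's test with pooled variance, giving about 77% and 87%. The protocol must then name the outcome and time point to which it applies.
3. Write the same alpha rule into the analysis paragraph, which now says only p < 0.05, and say how the comparisons with control follow from the ANOVA.

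This costs one rerun of the calculation and edits to the wording, with no extra subjects. The price is that stated power for A falls below 80%. If the sponsor wants to keep 80% for both comparisons under Bonferroni, the cost is 17 enrolled per arm, 51 instead of 45. If the sponsor prefers per-comparison testing, the Bonferroni and overall-error wording must go and the familywise error of about 9% should be stated.

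### Section 4.1 names single-step Bonferroni for the two comparisons with control, which leaves group A at 74% power; Holm keeps the same 5% for those two tests and gives 81–82% if both planned effects hold

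*Combined protocol and SAP*

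**What the plan says.** Section 4.1 of the combined protocol and SAP deals with these comparisons in three places.

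- **Software output table (PASS).** The Bonferroni setting is "none (divisor = 1"), and each row carries alpha 0.05. Power at 13 per arm is given as 0.83233 for A vs control and 0.91287 for B vs control.
- **Summary statements.** "The hypotheses are evaluated using two two-sided, two-sample methods"; these are then described as "Bonferroni-adjusted t-tests with the same variance and an overall (experimental) Type I error rate" of 0.05. The planning values follow: "The common standard deviation for all groups is assumed to be 2.1", "The mean value of the control group is assumed to be 4.72", and "The treatment means 2.21 and 1.87 with at least 80% test strength to be detected in each case".
- **Statistical approach to examine the primary endpoints.** This paragraph plans a repeated-measures ANOVA (time by group) at p < 0.05 for all recovery parameters. It names no contrast with control, no t-test and no multiplicity adjustment.

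Bonferroni is the only multiplicity method named in the document. Holm is not mentioned.

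**The concern.** Single-step Bonferroni tests both p values at 0.025. Holm tests the smaller at 0.025 and, if that passes, the larger at 0.05. Both hold the overall error for the two tests at 5%, and Holm rejects everything that Bonferroni rejects. The planning values assume that both cooling arms work (2.21 and 1.87 against 4.72), and that is where the single-step rule gives away the most power.

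At stake is the plan's own target. The method named in the summary statement does not deliver 80% for A at the stated sample size. The table hides this because it was run without the correction.

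**Working it through.** **Inputs, all from section 4.1:** n = 13 per arm; SD 2.1; differences 4.72 − 2.21 = 2.51 (A) and 4.72 − 1.87 = 2.85 (B); two-sided equal-variance t-tests; overall alpha 0.05.

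**Formula.** The noncentrality is δ / (σ√(2/n)), with σ√(2/n) = 2.1 × √(2/13) = 0.8237.
- A: 2.51 / 0.8237 = 3.047
- B: 2.85 / 0.8237 = 3.460

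Power is the probability that a noncentral t on 24 df exceeds the critical value in absolute size.

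**Step 1: reproduce the plan's figures.** At alpha 0.05 (critical value 2.064), power is 0.83233 for A and 0.91287 for B, which matches the table to five decimals. With 12 per arm, A has 0.799, so 13 is the smallest size that meets 80% without correction.

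**Step 2: apply the Bonferroni method that the text names.** At alpha 0.05/2 = 0.025 (critical value 2.391), power is 0.740 for A and 0.850 for B. A would need 15 evaluable subjects per arm to reach 80% (0.811).

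**Step 3: Holm.** A is rejected if p_A < 0.025, or if p_B < 0.025 and p_A < 0.05. The two tests share the control arm, so this was simulated (1,000,000 trials for the planned effects and for the global null; 300,000 to 400,000 for the other cases). For A, the second route adds 0.811 − 0.740 = 0.071.

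| At 13 per arm, planned effects | A vs control | B vs control |
|---|---|---|
| No correction (printed table) | 83.2% | 91.3% |
| Bonferroni, two-sample t (24 df) | 74.0% | 85.0% |
| Holm, two-sample t (24 df) | 81.1% | 88.3% |
| Bonferroni, pooled variance (36 df) | 75.8% | 86.4% |
| Holm, pooled variance (36 df) | 82.3% | 89.2% |

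The chance that both comparisons succeed (two-sample) rises from 67% to 78%.

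**Step 4: error rate.** Under the global null, the chance of any false positive is about 4.6% for both methods, because Holm's first step is Bonferroni. When one null is true and the other arm has its planned effect, the false-rejection rate under Holm is at most about 4.5%.

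**Step 5: how far the gain for A depends on the assumptions.**

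| Scenario (Holm, 13 per arm) | A, two-sample | A, pooled |
|---|---|---|
| Planned effects, SD 2.1 | 81% | 82% |
| Both arms at A's effect | 79.6% | 81% |
| B has no effect | 74% | 76% |
| Planned effects, SD 2.39 | 69% | 71% |
| A vs B added to the Holm family | 73% | 75% |

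The SD of 2.39 is the one that section 4.1 and the synopsis attach to the initial VAS score.

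**The case against.** **The amended sentence sits in the sample-size part.** The analysis paragraph and the synopsis name only a repeated-measures ANOVA, so rewording the summary statement alone would not change what is analysed. This stands and shapes the fix. It does not make the point irrelevant: an ANOVA does not say which arm differs from control, and the hypotheses in section 2.1 need that comparison.

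**The 74% is not printed anywhere.** The document states 83% and 91%. A reader might infer that Holm raises power above the plan's figures. It does not: 81% and 88% are lower than the printed values. The gain is relative to the Bonferroni wording only.

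**The 5% covers little.** A reader might infer that Holm settles the trial's multiplicity. It covers two contrasts on one outcome. Section 2.1 also asks about immediate versus delayed cooling, and section 2.2 lists several primary endpoints. Adding A vs B to the Holm family brings A back to 73–75%.

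**The gain is conditional.** A reader might infer that Holm secures 80% for A. The sensitivity table shows otherwise. The stated mean reduction of 47% would also put both arms at 4.72 × 0.53 = 2.50, whereas the table's 2.21 is a 53% reduction; at 2.50 and SD 2.1, two-sample Holm gives about 68%.

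**Other routes exist.** With three groups, an overall F-test followed by unadjusted pooled pairwise tests also holds 5% on a single outcome, covers A vs B, and gives about 82% and 89%. This is a fair alternative, but the plan does not specify it either.

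**Bonferroni is valid, and 15 per arm are enrolled.** With 15 evaluable, Bonferroni gives A 81%. But the plan sizes on 13 after 10% dropout, and section 4.2 does not replace drop-outs. Securing 15 evaluable would take 15 / 0.9 = 16.7, so 17 per arm, or 51 subjects instead of 45.

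**Conclusion.** The point holds as one of efficiency and consistency. Under the Bonferroni method that section 4.1 names, A vs control has 74% power (76% pooled) at 13 per arm, about 6 points (4 pooled) below the target of "with at least 80% test strength to be detected in each case". For the two control comparisons, Holm holds the same 5%, never rejects less, and brings power to 81% and 88% (82% and 89% pooled).

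This rests on both planned effects being real, on SD 2.1, on 13 evaluable per arm, and on a family limited to these two contrasts on one outcome. The documents do not support reading it as an error-control failure of Bonferroni, as an assurance of 80% for A in all circumstances, or as a remedy for the comparison of A with B or for the other primary endpoints.

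**What to change.** 1. In the summary statement of section 4.1, replace the Bonferroni-adjusted t-tests with Holm-adjusted tests of A vs control and B vs control, using the variance pooled over the three groups, at an overall two-sided 5%.
2. In the paragraph on the statistical approach to the primary endpoints, name the same two Holm-adjusted contrasts as the follow-up to the repeated-measures ANOVA. Without this, step 1 changes nothing in the analysis.
3. Reconcile the power table and its no-correction setting with the text. State 82% (A) and 89% (B) at 13 per arm for the soreness VAS and these two comparisons only, on the assumption that both planned effects hold at SD 2.1. Add the value for A if B has no effect (76%) and at SD 2.39 (71%).
4. State that A vs B and the other primary endpoints lie outside this 5% family.

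The cost is a few sentences, with no added subjects and no looser error rate for the two comparisons. The small downside is that Holm has no simple matching simultaneous confidence intervals; ordinary 95% intervals can be shown if they are labelled unadjusted.
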